6.1.4 Treatment assignment

Approximately 50 subjects aged \geq 55 years will be randomized (i.e., enrolled) in a 1:1 ratio to either sequence. No stratification will be applied.

After verifying that the subject meets all inclusion criteria and that none of the exclusion criteria are violated, the investigator / authorized delegate contacts the IRT system at Visit 2 to randomize the subject. The IRT system assigns the treatment kit number to the subject, which matches the treatment arm assigned by the randomization list to the randomization number.

The IRT system is handled by an external independent vendor who will generate the randomization list.

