## 2 STUDY DESIGN AND FLOW

This is a post-approval, multi-center, double-blind, randomized, placebo-controlled, 2-way cross-over study assessing daridorexant at a dosing regimen of 50 mg, once daily, vs placebo over a 4-week treatment period in adult subjects of 55 years and older with insomnia and comorbid nocturia.

[figure not shown]
Approximately 50 subjects will be randomized in a 1:1 ratio to one of two treatment sequences: daridorexant 50 mg / placebo or placebo / daridorexant 50 mg.

The study will be conducted at approximately 18 sites in the United States, Spain, and Germany.

The study design is shown in Figure 1.

Page 9/50

Figure 1 Study design for ID-078A401

- The voiding diary is completed on 3 consecutive days following V1, V2 and V6 and on the 3 days immediately preceding V4 and V8
- <--> Daily completion of sleep diary from V1 to V8

D = day; EOS = end-of-study; EOTP = end-of-treatment period; V = visit.

The study comprises the following 5 periods: the screening period, TP I, washout period, TP II, and the safety follow-up period.

The **screening period** starts with the signing of the informed consent form at Visit 1 and ends with Randomization at Visit 2 or with a screening failure. It lasts 14–21 days.

**TP I** starts with the administration of the first dose of study treatment and ends on the day after the last dose of study treatment (Day 29). The study subjects will be treated for 4 weeks.

The **washout period** starts after completion of the TP I and lasts 14–21 days. During the washout period the subjects will not be treated at all and will be followed up for safety (5–10 days).

**TP II** starts with the administration of the first dose of the 'other' study treatment and ends on the day after the last dose of study treatment (Day 29). The study subjects will be treated for another 4 weeks.

The **safety follow-up period** starts on the day after the last dose of study treatment in TP II and ends at the EOS visit (5–10 days after EOTP II).

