### 6.1.3 Statistical model

Changes from baseline to post-baseline visits in sTST will be analyzed using an MMRM with treatment (daridorexant 50 mg; placebo), period (TP I; TP II), week within period (Week 1; Week 2; Week 3; Week 4), the interaction of treatment and week as factors, and baseline sTST assessment as covariate.

An unstructured covariance matrix will be used to account for the correlation between repeated measurements from the same subject. This approach relies on the missing at random assumption. A restricted maximum likelihood approach in combination with the Newton Raphson Algorithm will be used to derive (unbiased) estimates of variance components. The Kenward-Roger approximation will be used to compute the denominator degrees of freedom and adjust standard errors [Kenward 1997]. If the analysis fails to converge, the following structures will be tested in the subsequent order until model-convergence is achieved: heterogeneous Toeplitz, Toeplitz, autoregressive, and compound symmetry.

To evaluate the efficacy hypotheses, appropriate contrasts will be used to test the treatment differences of interest (i.e., the difference in LS Mean change from baseline to Week 4 between daridorexant 50 mg and placebo).

The LS Mean for each treatment per time point will be displayed along with its associated standard error and 95% CI. For the daridorexant comparison with placebo, the placebo-adjusted LS Mean will be displayed along with the associated standard error, 95% CI and unadjusted 2-sided p-value. The null hypothesis will be rejected if the 95% CI for this difference excludes 0.

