# 6.3.2.2 Within-subject comparison of time to the first nocturnal void

#### 6.3.2.2.1 Variable

The time to first nocturnal void is derived as described in Section 6.3.2.1.1 (for Week 1 and Week 4). As each subject receives both treatments, a within-subject comparison of the time to first nocturnal void is performed, separately at Week 1 and Week 4, i.e., the 'preferences' (= longer average duration to first nocturnal void across 3 cycles) are summarized in a  $2 \times 2$  contingency table, as shown in Table 4. If a subject is missing data in one or both treatment periods, this subject's information is considered as missing and will not be included in the analysis. In the event of censored data, i.e., subjects that have no single void in 3 cycles, the preference will be assigned to the period where the subject was censored.

Page 26/50

Statistical Analysis Plan for Clinical Study Report Version 2 Doc No D-24.149

Table 4 Contingency table of preferences

Treatment	preference
Heatinent	preference

Treatment group	TP I	TP II	Total
Daridorexant 50 mg	х	у	x + y
Placebo	Z	a	z + a
Total	x + z	y + a	x + y + z + a

TP I/II = treatment period I/II

From this table it can be derived that (x + y) subjects prefer daridorexant 50 mg, whereas (z + a) subjects prefer placebo. The differences across periods can be observed in the total row (x + z) for TP I; y + a for TP II).

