# 6.3.2.2.2 Analysis

The contingency table is analyzed separately at Week 1 and Week 4 based on the FAS via a 2-sided sign test for matched pairs. A binomial distribution will be used to compute the p-values (2-sided), which will be presented in the table.

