# 6.3.2.5.2 Analysis

Changes from baseline to post-baseline visits in the number of nocturnal voids will be analyzed using an MMRM with treatment (daridorexant 50 mg; placebo), week within period (Week 1; Week 4), and period (TP I; TP II) as factors, baseline number of nocturnal voids as covariate, and the interaction of treatment and week. The MMRM will be applied to all 3 approaches, as described above.

An unstructured covariance matrix will be used to account for the correlation between repeated measurements from the same subject. A restricted maximum likelihood approach in combination with the Newton Raphson Algorithm will be used to derive (unbiased) estimates of variance components. The Kenward-Roger approximation will be used to compute the denominator degrees of freedom and adjust standard errors [Kenward 1997]. If the analysis fails to converge, the following structures will be tested in the subsequent order until model-convergence is achieved: heterogeneous Toeplitz, Toeplitz, autoregressive, and compound symmetry.

To evaluate the efficacy hypotheses, appropriate contrasts will be used to test the treatment differences of interest (i.e., the difference in LS Mean change from baseline to Week 4 between daridorexant 50 mg and placebo).

The LS Mean for each treatment per time point will be displayed with the associated standard errors and 95% CIs. For the comparison of daridorexant with placebo, the placebo-adjusted LS Mean will be displayed with the associated standard error, 95% CI and unadjusted 2-sided p-value.

The changes from baseline in the total number of nocturnal voids will be plotted over time (averaged across the 3 nights) by treatment (based on all 3 approaches).

The number of nocturnal voids and the change in the number of nocturnal voids will be analyzed descriptively, averaged across the 3 voiding nights, by treatment and visit (based on all 3 approaches).

Descriptive analyses will be repeated for the number of daytime voids, based on the data provided by Minze Health, by treatment and visit.

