# 6.3.3.6 Treatment satisfaction

The Numeric Rating Scale collects information regarding treatment satisfaction during the clinical trial by asking the subjects to mark the number that best describes overall satisfaction on a scale from 0 ('Not at all satisfied') to 10 ('Extremely satisfied). Self-reported treatment satisfaction is assessed on the morning of Visit 4 and Visit 8 on the eDiary.

A paired t-test will be applied to the within-subject differences (daridorexant 50 mg vs placebo) to test for differences between the two treatments. The output will contain the mean estimate (including 95% CI) and the associated p-value.

Treatment satisfaction will be summarized descriptively by treatment.

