## 6.3.3.7 Treatment preference

The subjects will be asked at Visit 8 to select which treatment period (TP I or TP II) was preferred and complete it on the eDiary. Subjects that were not treated in TP II will be excluded from analysis.

Treatment preference will be summarized descriptively, overall and by treatment sequence. Odds ratios (including 95% CIs) and associated p-values will be added to the output.

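### The treatment-satisfaction t-test and, less importantly, the first-void sign test ignore period: power is lost if a period effect exists, and the estimate is biased only if the analysed sequences are also unequal

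*SAP*

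**What the plan says.** SAP 6.3.3.6 rates satisfaction from 0 to 10 at Visit 4 and Visit 8 and tests it as follows: "A paired t-test will be applied to the within-subject differences (daridorexant 50 mg vs placebo"). The output is a mean estimate, 95% CI and p-value.

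SAP 6.3.2.2.1 scores each subject by the treatment with the longer average time to first nocturnal void and cross-classifies this by treatment period in Table 4. The period information is only for inspection: "The differences across periods can be observed in the total row". SAP 6.3.2.2.2 then analyses the table "via a 2-sided sign test for matched pairs", with binomial p-values, separately at Week 1 and Week 4.

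Elsewhere the SAP adjusts for period. The primary model in 6.1.3 is fitted "with treatment (daridorexant 50 mg; placebo), period (TP I; TP II), week within period". The nocturnal-voids model in 6.3.2.5.2 has "week within period (Week 1; Week 4), and period (TP I; TP II) as factors". The ISI, VAS and IDSIQ models refer back to 6.1.3. On preference, 6.3.3.7 says: "Treatment preference will be summarized descriptively, overall and by treatment sequence".

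On allocation, SAP Section 2 states: "Approximately 50 subjects will be randomized in a 1:1 ratio to one of two treatment sequences". Protocol 6.1.4 adds: "No stratification will be applied". Neither document says whether blocks are used.

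**The concern.** In a two-period cross-over, a period effect enters the daridorexant-minus-placebo difference with opposite signs in the two sequences. A test that pools the differences treats that systematic split as noise. If one sequence also contributes more subjects, the two contributions no longer cancel and the remainder is attributed to treatment.

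A period effect on satisfaction is conceivable. The Visit 4 rating is given before the subject has any comparator, and the Visit 8 rating after both treatments. The stability rationale in Protocol 4.3 covers disease status, not rating behaviour. For first void, SAP 6.3.2.2.1 drops any subject lacking data in either period, so the analysed sequences may differ in size even if randomisation was balanced. At stake are the precision, and possibly the accuracy, of two reported comparisons. The SAP gives no reason for treating them differently from its models.

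**Working it through.** **The plan's own figure.** No power is stated for satisfaction or for the sign test. The stated paired t-test power is for sTST (Protocol 9.4) and it reproduces. With N = 50, 26/44 × √50 = 4.18 gives 98.4% (stated: at least 90%), and 20/44 × √50 = 3.21 gives 88.3% (stated: at least 80%).

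**Inputs.** N = 50 and 1:1 allocation come from the documents. The rest is assumed, in units of the SD of the within-subject difference: treatment effect τ = 0.42 (0.404 would give 80% power at N = 50) and period effect π (Period II minus Period I) of 0, 0.25 or 0.5. DP is daridorexant first, PD is placebo first.

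**Satisfaction, formulas.** The expected daridorexant-minus-placebo difference is τ − π in DP and τ + π in PD. Hence:

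- Bias of the pooled mean = π × (n_PD − n_DP)/N. This is zero if either factor is zero.
- Expected sample variance of the pooled differences = 1 + 4π² n_DP n_PD / [N(N − 1)]. The true standard error of the pooled mean stays at 1/√N, so the test uses too large a standard error.
- Approximate unadjusted power = Φ[(τ + bias)√N − 2.010 × inflated SD].
- Adjusted power = Φ[τ/SE − 2.011], with SE = ½√(1/n_DP + 1/n_PD).

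**Numbers.**

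- 25/25, π = 0.25: SD 1.031; Φ(2.970 − 2.073) = 81%. Adjusted: Φ(2.970 − 2.011) = 83%.
- 25/25, π = 0.5: SD 1.120; Φ(2.970 − 2.251) = 76%. Adjusted: 83%.
- DP 28, PD 22, π = 0.5: bias 0.5 × (−6)/50 = −0.06; SD 1.119; Φ(0.36 × 7.071 − 2.249) = 62%.
- DP 22, PD 28, π = 0.5: bias +0.06; Φ(0.48 × 7.071 − 2.249) = 87%.
- Adjusted at either 28/22 split: SE 0.1424; Φ(2.948 − 2.011), about 83%.

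Simulation agrees to within about a point.

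**Simulated type I error of the unadjusted t-test.** At 25/25 it is 4.4% at π = 0.25 and 2.8% at π = 0.5, so the test is conservative. At 28/22 and π = 0.5 it stays below 5%. It takes 30/20 with π = 0.5 to reach 7.0%, against about 5% adjusted.

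**No period effect.** At 25/25 the two analyses have the same power. At 30/20 (τ = 0.404) the unadjusted test has 80% and the adjusted test 78%, with no bias in either.

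**First void.** Exact enumeration with a treatment log-odds of 0.85 (about 70% favouring daridorexant), at 25/25:

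| Period log-odds | Sign test | Mainland-Gart (Fisher) |
|---|---|---|
| 0 | 78.5% | 78.5% |
| 0.5 | 74.0% | 74.1% |
| 1.0 | 59.1% | 62.0% |

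The gain is 0 to 3 points at the planned split. At 30/20 and period log-odds 0.5 it depends on direction. With more subjects on daridorexant first, the sign test has 62.4% against 76.2%. With more on placebo first, it has 83.7% against 75.7%.

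**Reading Table 4 by sequence.** A daridorexant preference in TP I (x) can only come from DP, and one in TP II (y) only from PD. Likewise a placebo preference in TP I (z) is PD and in TP II (a) is DP. The sequence table is therefore DP: x vs a, and PD: z vs y.

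**The case against.** The strongest case for leaving the plan alone is that both tests are legitimate within-subject tests of exploratory endpoints, outside the single controlled hypothesis. The plan expects stable disease, uses a 14–21 day washout and anticipates under 3% dropout. No document supplies a period effect, and 0.5 SD is larger than the assumed treatment effect. At 0.25 SD and equal sequences the t-test loses only about 2 points. Table 4 shows the period totals openly. All of this stands and keeps the severity low. One limit is that the dropout figure does not bound missing first-void pairs: a missing bedtime or waketime sets the variable to missing (SAP 6.3.2.1.1), and only completed cycles count (SAP 6.3.2).

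Four stronger readings are tempting but unsupported:

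- **That unequal sequences alone cause bias.** The bias is a product and needs a period effect as well.
- **That the adjusted tests always have more power.** When the imbalance favours daridorexant, the unadjusted test rejects more often (87% against about 83%), partly because its estimate is biased upwards. That is an estimation problem, not a power advantage.
- **That the current tests inflate false positives.** At equal sequences they are conservative. Inflation needs a marked imbalance together with a sizeable period effect.
- **That such imbalance is to be expected.** Under simple randomisation of 50, a split of 30/20 or worse has probability 20%, but the documents do not say that simple randomisation is used.

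**Conclusion.** The point holds as a low-severity matter of efficiency and robustness, mainly for satisfaction. Two inferential analyses omit a design factor that the SAP's mixed models include. Over an assumed period effect of 0.25 to 0.5 SD, with equal sequences, the paired t-test gives up about 2 to 7 points of power and its estimate stays unbiased. The sign test gives up 0 to 3 points over its own assumed range. A 28/22 split at 0.5 SD adds a satisfaction bias of 0.06 SD in either direction. These sizes rest wholly on assumed period and treatment effects. With no period effect, nothing is lost under the current plan. The primary analysis is not affected.

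**What to change.** **SAP 6.3.3.6.** Make the main comparison a two-sample t-test between sequences on each subject's Period I minus Period II difference. Halve the between-sequence difference and its confidence limits to obtain the treatment difference and 95% CI. A model with subject, period and treatment is equivalent.

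**SAP 6.3.2.2.2.** Use the Mainland-Gart test, with Fisher's exact p-value, on Table 4 rearranged by sequence: daridorexant first, x vs a; placebo first, z vs y. The rearrangement must be written into the SAP, because Fisher's test on Table 4 as laid out does not test treatment.

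Keep the paired t-test and the sign test as sensitivity analyses, and report the number analysed per sequence.

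**Cost.** Two SAP sentences, a few lines of code and no new data. The adjusted t-test uses one degree of freedom and gives up at most about 2 points of power when there is no period effect and the sequences are unequal (80% against 78% at 30/20).

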## 6.3.3.7 Treatment preference

The subjects will be asked at Visit 8 to select which treatment period (TP I or TP II) was preferred and complete it on the eDiary. Subjects that were not treated in TP II will be excluded from analysis.

Treatment preference will be summarized descriptively, overall and by treatment sequence. Odds ratios (including 95% CIs) and associated p-values will be added to the output.

#### 7 SAFETY VARIABLES AND ANALYSES

# 7.1 Overview of safety analyses

The SAF will be used for tables and listings of safety data, unless otherwise stated.

Unless otherwise noted, only the treatment-emergent safety data will be considered in tables and figures.

All safety data described below will be listed.

#### 7.2 Adverse events

TEAEs are defined as AEs that started or worsened on or after study treatment start date up to the EOT + 5 days (in each treatment period). AEs that start in TP I and continue into TP II will only be presented as TP I AEs, unless there is a worsening in TP II. AEs that start in the washout period (i.e., on day 6 of the washout period up to 1 day prior to start of TP II) and continue into TP II will not be presented for any of the treatment periods.

AEs will be coded using MedDRA. The MedDRA version used for reporting will be specified in the footnote of the applicable output.

The number (%) of study subjects experiencing a TEAE (including SAEs, AESI, and AEs leading to premature discontinuation and/or temporary interruption of study treatment) will be summarized by SOC and/or PT, and/or maximum intensity.

AESIs, defined as AE PTs denoting 'falls' and 'incontinence episodes' will be summarized separately.

A subject with multiple intensities reported for an AE will be summarized under the maximum intensity recorded for the event.

Apart from the summaries of occurrences, where each event is counted, a subject with multiple occurrences of an AE is counted only once in the AE category (e.g., SOC, PT). If a single AE worsens on the same treatment, this event will be considered as one occurrence.

AEs will be sorted by descending frequency, first based on daridorexant 50 mg, then based on placebo. After this sorting, SOCs are presented in alphabetical order and PTs are sorted alphabetically within each SOC.

The following AE summary tables will be provided:

- Treatment-emergent AEs;
- TEAEs related to study treatment;

Page 35/50

Statistical Analysis Plan for Clinical Study Report Version 2 Doc No D-24.149

- AEs leading to premature discontinuation of study treatment;
- AEs leading to temporary interruption of study treatment;
- Treatment-emergent SAEs (including occurrences);
- Treatment-emergent SAEs related to study treatment (including occurrences);
- TEAEs with fatal outcome;
- TEAEs related to study treatment with fatal outcome;
- Total number of deaths;
- Treatment-emergent AESIs;
- AEs during the washout period.

All AEs will be listed, with AESIs and SAEs being flagged in the AE listing.

Separate listings will be provided for AEs leading to premature discontinuation of study treatment, AEs leading to temporary interruption of study treatment, SAEs, fatal AEs, and AESIs.

All deaths will be listed, with cause of death, using the SCR.

An AE listing, using the SCR, will also be provided for study subjects who were not randomized (i.e., screen failures) and study subjects who were randomized but did not take study treatment. This listing will therefore include any study subjects who discontinued the study due to an AE but did not receive any study treatment.

Any other summary required for disclosure to the public database will be generated as appropriate.

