	 b) Occurrence of suicidal ideation, suicidal behavior, and/or self-injurious behavior with/without suicidal intent based on the Columbia Suicide Severity Rating Scale[©] (C-SSRS[©])
	c) Morning sleepiness as determined by morning sleepiness VAS.
DESIGN	Multi-center, double-blind, randomized, placebo- controlled, 2-way cross-over, post-approval study.
	The study consists of 2 treatment periods (I and II) of 29 days each, separated by a 14–21 day washout period.
ENDPOINTS	 Primary efficacy endpoint Change from baseline to Week 4 in sTST in each treatment period

	Baseline is the mean value based on the screening sleep diary for sTST, which must be performed on each of the 7 days preceding Randomization.
	Week 4 is the mean value based on the sleep diary entries for sTST performed on study days 23–29 of each period.
	Other efficacy endpoints
	Other endpoints are listed in the main body of the protocol.
	Safety endpoints
	Safety monitoring will include:
	• Occurrence of treatment-emergent AEs up to 5 days after End-of-Treatment Period I (EOTP I) and/or End-of-Treatment Period II (EOTP II).
	• Occurrence of treatment-emergent AESIs up to 5 days after EOTP I and/or EOTP II.
	• Occurrence of treatment-emergent serious AEs up to 5 days after EOTP I and/or EOTP II.
	• Occurrence of treatment-emergent AEs leading to premature discontinuation of the study and/or treatment.
	• Change from baseline to EOTP I and EOTP II in vital signs (systolic blood pressure, diastolic blood pressure, and pulse rate).
	• Change from baseline to EOTP I and EOTP II in morning sleepiness as determined by the scores on the VAS in the morning.
	• Occurrence of suicidal ideation, suicidal behavior, and/or self-injurious behavior with / without suicidal intent based on the C-SSRS [©] at Visit 1, Visit 4, Visit 5, Visit 8, and Visit 9.
PERIODS	Screening period: Starts with the full signature of the informed consent form (ICF) at Visit 1 and lasts 14–21 days. All baseline assessments as well as eligibility checks will be done during this period.
	Treatment period (Periods I and II): Randomization will take place on Day 1 (Visit 2) after confirmation that all eligibility criteria have been met, prior to the first study drug

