Daridorexant (ACT-541468) Insomnia and comorbid nocturia Protocol ID-078A401 Version 3

4 September 2023, page 44/122

Objectives	Endpoints in period I and period II			
	• Changes from baseline to Week 1, Week 2, Week 3, and Week 4 in Patient Global Impression of Change (daytime and nighttime symptoms)			
	 Change from baseline to Week 4 in Patient Global Assessment of Disease Severity (daily life) Change from baseline to Week 4 in Patient Global Impression of Change (daily life) 			
	• Change from baseline to Week 2 and Week 4 in EQ-5D-3L score			
	• Treatment satisfaction at Week 4 assessed via NRS			
	• Treatment period preference at Visit 8 (EOTP II)			
To explore a) the sensitivity of the IDSIQ to detect clinical changes in this study population and b) the use of narratives to report subject's perception of treatment effect	 The change from baseline to Week 1, Week 2, Week 3, and Week 4 in all IDSIQ domains The subjects will be asked to complete a narrative at the end of each treatment period. More details on the analysis will be provided in the SAP. 			
To assess the safety and tolerability of daridorexant	Safety endpoints			
	Safety monitoring will include:			
	• Occurrence of TEAEs up to 5 days after EOTP I and/or EOTP II.			
	• Occurrence of treatment emergent AESIs up to 5 days after EOTP I and/or EOTP II.			
	• Occurrence of treatment-emergent serious adverse events up to 5 days after EOTP I and/or EOTP II.			
	Occurrence of TEAEs leading to premature discontinuation of the study and/or treatment.			
	• Change from baseline to EOTP I and EOTP II in vital signs (systolic blood pressure, diastolic blood pressure, and pulse rate).			
	• Change from baseline to EOTP I and EOTP II in morning sleepiness as determined by the scores on the VAS in the morning.			
	• Occurrence of suicidal ideation, suicidal behavior, and/or self-injurious behavior with / without suicidal intent based on the C-SSRS [©] at Visit 1, Visit 4, Visit 5, Visit 8, and Visit 9.			

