9.2.5.1.2 AEs leading to premature discontinuation of study treatment

AEs leading to premature discontinuation of study treatment will be summarized in a similar manner as those described in Section 9.2.5.1.1.

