# 5.1.2 Study disposition

Study subject disposition will be summarized based on the SCR, presented by treatment sequence and overall, and will include:

- Number of study subjects screened (only for overall column).
- Number (%) of study subjects randomized (based on non-missing randomization number).
- Number (%) of study subjects who received study treatment during the TP I (based on non-missing 'Treatment start date' for TP I on the 'Study Treatment Log' page). Percentage will be based on randomized subjects.
- Number (%) of study subjects who received study treatment during the TP II (based on non-missing 'Treatment start date' for TP II on the 'Study Treatment Log' page). Percentage will be based on randomized subjects.
- Number (%) of study subjects who completed TP I (based on 'Reason for treatment stop' entered as 'Completion as per protocol' for TP I on the 'Study Treatment Log' page). Percentage will be based on study subjects who received study treatment (in TP I).
- Number (%) of study subjects who completed the TP II (based on 'Reason for treatment stop' entered as 'Completion as per protocol' for TP II on the 'Study Treatment Log' page). Percentage will be based on study subjects who received study treatment (in TP II).
- Number (%) of study subjects completing the study (based on 'Did the subject complete the study?' recorded as 'Yes' on the 'End of Study Status' page). Percentage will be based on randomized subjects.
- Number (%) of study subjects completing the washout-period, i.e., subjects being treated in TP I and TP II.

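### The protocol's safety endpoint covers TEAEs leading to discontinuation of the study and/or treatment, but the planned AE outputs cover discontinuation of treatment only

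*SAP*

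**What the plan says.** The endpoint is stated twice in the protocol. Table 3 in Section 3.4 gives "Occurrence of TEAEs leading to premature discontinuation of the study and/or treatment" and the synopsis gives "Occurrence of treatment-emergent AEs leading to premature discontinuation of the study and/or treatment".

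The analysis sections are narrower. Protocol 9.2.5.1.2 states: "AEs leading to premature discontinuation of study treatment will be summarized in a similar manner as those described in Section 9.2.5.1.1". In SAP 7.2 the list of AE summary tables has the entry "AEs leading to premature discontinuation of study treatment", and for listings the section says "Separate listings will be provided for AEs leading to premature discontinuation of study treatment". Neither document plans an AE table or listing for discontinuation of the study.

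The SAP 7.2 treatment-emergence window is "TEAEs are defined as AEs that started or worsened on or after study treatment start date up to the EOT + 5 days", applied in each treatment period.

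On disposition, SAP 5.1.2 counts completion of Period I "based on 'Reason for treatment stop' entered as 'Completion as per protocol' for TP I". SAP 5.1.3 identifies premature treatment discontinuation from the same log field, entered as a discontinuation. Separately, SAP 5.1.3 tabulates premature study discontinuation by primary reason on the RND and FAS, repeats that table by study period and treatment with the washout as its own category, and lists all reasons.

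**The concern.** The protocol does not treat stopping treatment and leaving the study as the same event: Section 5.9.1 says that a subject who stops treatment early is not considered withdrawn. The two parts of the endpoint therefore need separate handling, and only the treatment part has an AE-level output.

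A cross-over has a route out of the study that a parallel-group trial lacks. A subject can finish the first treatment as planned and then decline the second because of an adverse event on the first. That is a tolerability failure of the first treatment, but no course of treatment has been cut short. If the AE-leading-to-discontinuation table is restricted to treatment discontinuation, it can understate AE-related withdrawal for the treatment that caused it, and it does not match the endpoint that the protocol states.

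**Working it through.** The documents give no figure for this output to reproduce, so the check is a comparison of passages, followed by one line of arithmetic on size.

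**Side by side**

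| Place | Discontinuation of treatment | Discontinuation of study |
|---|---|---|
| Protocol synopsis and Table 3 (endpoint) | yes | yes |
| Protocol 9.2.5.1.2 (analysis) | yes | no |
| SAP 7.2, AE tables by SOC/PT | yes | no |
| SAP 7.2, separate AE listings | yes | no |
| SAP 5.1.3, disposition by primary reason | yes (SAF) | yes (RND and FAS) |

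The narrowing therefore begins inside the protocol, between its endpoint table and its analysis section, and the SAP carries it forward. Protocol 9.2.6 leaves the full description of other safety analyses to the SAP, so the SAP was a natural place to close the gap.

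**Tracing one subject**

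1. The subject has an AE that starts during Period I or within 5 days after the end of treatment. By SAP 7.2 it is a TEAE of Period I and is counted in the general TEAE table under the Period I treatment.
2. Period I dosing is finished, so the treatment log shows completion as per protocol. By SAP 5.1.2 the subject completed TP I. By SAP 5.1.3 there is no premature treatment discontinuation.
3. The subject withdraws during the 14–21 day washout because of that TEAE. Period II treatment never starts, so there is no TP II log entry to mark as a discontinuation.
4. The event meets the protocol endpoint, because a TEAE led to premature discontinuation of the study.
5. The event does not enter the SAP 7.2 table or listing of AEs leading to discontinuation of study treatment, unless the site records it as a treatment discontinuation.
6. The subject is counted in the SAP 5.1.3 study-discontinuation tables under the washout, with the recorded primary reason, and appears in the listing of reasons.

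**What step 6 does not supply**

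- The SAP 5.1.3 tables give a reason for leaving. They do not give the SOC or PT, or say whether the event was treatment-emergent.
- They are on the RND and FAS. Under SAP 4.1.3, FAS subjects are evaluated as assigned. SAP 4.3 requires the safety set for safety endpoints, and SAP 4.1.5 defines that set by treatment received in each period.
- They are to be shown by treatment, but subjects are untreated in the washout (SAP Section 2), and SAP Section 5 says that each subject contributes to both treatment columns. No rule assigns a washout withdrawal to the Period I treatment.
- The SAP 7.2 table of AEs during the washout is not a discontinuation table. The same section describes washout-onset AEs as those starting from day 6 of the washout, which is after the TEAE window.

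**Size**

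Inputs: about 50 randomized subjects (protocol 4.1); expected dropouts below 3% (protocol 9.2.2.4, SAP 6.1.4).

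0.03 × 50 = 1.5, so fewer than 1.5 subjects, that is, at most one.

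One such subject would move the count for the treatment concerned from 0/50 = 0% to 1/50 = 2%, taking all 50 as treated with it. The planning figure covers dropout for any cause, so one is a ceiling under the plan's own assumption and not an estimate of how often this path will occur.

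**The case against.** The strongest reply is that nothing disappears. The subject has a cell in the SAP 5.1.3 table (washout, with reason), the AE is in the TEAE table, and SAP 7.2 lists all AEs. With about 50 subjects, someone reading the two listings together could usually see which event led to the withdrawal. This stands against any inference that such a subject is missed altogether or that AE-related withdrawal goes unreported. It does not supply the stated endpoint as a summary on the safety set, by term and by treatment received.

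A second reply is that SAP 7.2 does not say which field selects AEs for its discontinuation table. Protocol 8.2.1 has the AE form record the action taken with study treatment, and a site might enter a permanent discontinuation for an AE that stops a subject from starting Period II. The AE might then reach the existing table. This also stands: the eCRF specifications are not among the documents, so whether the table captures the event depends on site practice that the plan does not fix.

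A reader might also infer that SAP 11.1 is wrong to declare no change from the protocol's planned analyses. The documents do not support that. The analysis planned in protocol 9.2.5.1.2 concerns study treatment, and the SAP carries it out. The mismatch is between two sections of the protocol.

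Finally, the effect could be made to look larger by supposing two or more affected subjects. Two of 50 is 4%, above the dropout the plan expects from all causes together.

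**Conclusion.** The point holds as a mismatch between the endpoint and its analysis across both documents. The protocol's endpoint includes TEAEs leading to discontinuation of the study, and no planned AE table or listing covers that part. A subject who completes Period I and withdraws in the washout because of a Period I TEAE would be visible in the general TEAE table and in disposition, but not in the AE-leading-to-discontinuation output on the safety set.

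This assumes that the site does not record the event as a treatment discontinuation, and that the SAP 7.2 table follows the treatment-log definition used in SAP 5.1.2 and 5.1.3. Neither can be confirmed from the documents. The expected size is at most about one subject of 50. Efficacy analyses are unaffected. It is a minor improvement, worth making because it is cheap and brings the analysis into line with the stated endpoint.

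**What to change.** In SAP 7.2, change the table and the listing to TEAEs leading to premature discontinuation of study treatment and/or the study, by SOC and PT on the safety set. Attribute each event to the treatment received in the period of TEAE onset, so that a washout withdrawal due to a Period I TEAE goes to the TP I treatment. Align protocol 9.2.5.1.2 with the wording of Table 3 and the synopsis, and note the extension in SAP Section 11.

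Identify cases from the 'Study stopped due to' field on the End of Study Status page together with the AE record. The documents do not show whether that field offers an adverse event as a reason, or whether it can be linked to a particular AE. A case-by-case link, made before unblinding, may therefore be needed for the very few subjects affected.

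The cost is a wording change, minor programming and possibly a short manual review. The reported discontinuation rate may come out slightly less favourable.
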